| 
14. Adverse Events: Adverse events (AE) should be documented and recorded at each visit using National Cancer Institute (NCI) Common Terminology Criteria for Adverse Events (CTCAE) version 4.03. For serious adverse events (SAEs), the active reporting period to Pfizer or its designated representative begins from the time that the patient provides informed consent, which is obtained prior to the patient's participation in the study, ie, prior to undergoing any study-related procedure and/or receiving study treatment, through and including 90 calendar days after the last administration of the study treatment (Arm A) or 90 days after the EOT visit (Arm B). SAEs occurring to a patient after the active reporting period has ended should be reported to the sponsor if the investigator becomes aware of them; at a minimum, all SAEs that the investigator believes have at least a reasonable possibility of being related to study treatment are to be reported to the sponsor.
 |

| |
|---|
| 
AEs (serious and non-serious) should be recorded on the Case Report Form (CRF) from the time the patient has taken at least 1 dose of study treatment (Arm A) or from Cycle 1 Day 1 (Arm B), through and including 90 calendar days after the last administration of the study treatment (Arm A) or 90 days after the EOT visit (Arm B).
 
If a patient begins a new anticancer therapy, the AE reporting period for non-serious AEs ends at the time the new treatment is started. Death must be reported if it occurs during the SAE reporting period after the last dose of study treatment, irrespective of any intervening treatment.
 |
| 
15. Concomitant Medications/Treatments: Concomitant medications and treatments will be recorded for all patients from 28 days prior to the start of study treatment and up to 90 days after the last dose of study treatment (Arm A) or 90 days after the EOT visit (Arm B). If a patient begins a new anti-cancer therapy, reporting of concomitant medications should end at the time the new cancer therapy is started; see Section 5.9 for additional details. All concomitant medications will be recorded in the CRF including supportive care drugs (eg, anti-emetic treatment and prophylaxis), the drugs used to treat adverse events or chronic diseases, and non-drug supportive interventions (eg, transfusions).
 |
| 
16. Survival Assessment: All patients will be followed for survival and subsequent anticancer therapies every 3 months (± 14 days) after the last study clinic visit until death, end of the study, or patient withdrawal of consent, whichever comes first. These visits may be conducted in-clinic or by remote contact (eg, telephone). Additional timepoints to collect survival information may be requested by the Sponsor in preparation for interim and final analyses.
 |
| 
17. Patient-Reported Outcome Questionnaire: NCCN-FACT FBISI-18 and EQ-5D-5L are to be administered at the End of Treatment/Withdrawal visit and at the 30, 60 and 90 Day Follow-up Visits.
 |
| 
18. Banked Blood Biospecimens for Exploratory Assessments: Blood biospecimens (~24 mL) will be collected at the End of Treatment/Withdrawal visit and retained as whole blood, plasma, and serum (Prep D1: 4 mL K₂ EDTA whole blood collection optimized for DNA analysis; Prep B1: 10 mL K₂ EDTA blood for plasma preparation, and Prep B2: 10 mL blood for serum preparation), and retained in a biobank for exploratory biomarker assessments, unless prohibited by local regulation or by decision of the Institutional Review Board or Ethics Committee. See Section 7.5.2 and Section 7.6.
 |
| 
19. De Novo Tumor Biopsy: A de novo (ie, fresh biopsy) tumor sample should also be collected at End of Treatment/Withdrawal visit, unless clinically contraindicated. Tumor tissue from cytologic sampling (eg, fine needle aspiration, including formalin fixed, paraffin embedded [FFPE] cell pellet material) or bone metastases is not adequate and should not be submitted. The de novo biopsy should be formalin-fixed and paraffin-embedded as per routine procedures (see Laboratory Manual), and the resulting FFPE tissue block(s) should be submitted to the Central Laboratory. If an FFPE tissue block cannot be provided, 15 freshly cut unstained slides (10 minimum) will be acceptable.
 |
| 
20. Pharmacokinetics: Arm A ONLY: Blood samples (3.5 mL) for avelumab PK will be taken at the End of Treatment and 30 day Follow-up visits. Details are outlined in Section 7.3.
 |
| 
21. Anti-Avelumab Antibodies (Anti-Drug Antibodies, ADAs) and Neutralizing Antibodies (Nab): Arm A ONLY. One blood sample (3.5 mL) for anti-avelumab antibodies (and simultaneous pharmacokinetic draws for measurement of avelumab) will be collected at the End of Treatment and 30 day Follow-up visits. All the samples that are positive for ADA may also undergo characterization for Nab.
 |

PROTOCOL AMENDMENT 6: SCHEDULE OF ACTIVITIES FOR STUDY TREATMENT, END OF TREATMENT AND FOLLOW-UP PERIODS

| Visit Identifiers ¹ | Avelumab plus BSC (1 cycle = 4 weeks) | | End of Treatment/ Withdrawal (±3 days) ² | Short-Term Follow-Up ³ | | |
|---|---|---------------------|---|--|--|--|
| | Day 1 (±3 days) | Day 15 (±3 days) | | 30 days (±3 days) After Last Dose of Avelumab | 60 days (±3 days) After Last Dose of Avelumab | 90 days (±3 days) After Last Dose of Avelumab |
| Clinical Assessments | | | | | | |
| Physical Examination ⁴ | Assessment not required per protocol but may be performed as clinically necessary | | | | | |
| ECOG Performance Status ⁴ | Assessment not required per protocol but may be performed as clinically necessary | | | | | |
| Vital Signs ⁴ | Assessment not required per protocol but may be performed as clinically necessary | | | | | |
| Weight ⁵ | X | X | | | | |
| Contraception Check ^{4,6} | X | X | X | X | | |
| Laboratory Studies | | | | | | |
| Hematology ^{4,7} | X | X | X | X | X | X |
| Blood Chemistry ^{4,7} | X | X | X | X | X | X |
| Thyroid Function and ACTH Tests ^{4,8} | X (at odd number cycle only) | | X | X | X | X |
| Serum/Urine Pregnancy Test ^{4,9} | X | X | X | X | | |
| Urinalysis ⁴ | Assessment not required per protocol but may be performed as clinically necessary | | | | | |
| 12-Lead ECG ^{4,10} | Assessment not required per protocol but may be performed as clinically necessary | | | | | |
| Other Assessments | | | | | | |
| Tumor Assessments (including scans) ¹¹ | As per local standard of care and when progression is suspected | | | | | |
| Adverse Events ¹² | X | X | X | X | X | X |
| Concomitant Medications/Treatments ¹³ | Assessment not required per protocol but may be performed as clinically necessary | | | | | |
| Study Treatment | | | | | | |
| Avelumab ¹⁴ | X | X | | | | |

ACTH = adrenocorticotropic hormone; BSC = best supportive care; CR = crossover; ECG = electrocardiogram; ECOG = Eastern Cooperative Oncology Group

Footnotes for PROTOCOL AMENDMENT 6: SCHEDULE OF ACTIVITIES FOR SCREENING AND STUDY TREATMENT PERIOD

| | |
|-----|--|
| 1. | Visit Identifiers: All assessments will be performed prior to dosing with avelumab unless otherwise indicated. Acceptable time windows for performing each assessment are described in the column headers. Note: laboratory tests may be performed up to 3 days prior to the scheduled clinic visit so that results will be available for review. |
| 2. | End of Treatment/Withdrawal: Obtain these assessments if not completed in the prior week. |
| 3. | Short-Term Follow-up: All patients will be followed for safety every 30 days (± 3 days) through 90 days after the last dose of avelumab or until the time of initiation of a new anticancer treatment, whichever occurs first. |
| 4. | These data will not be captured in the CRF unless the findings support the reporting of an AE. |
| 5. | Weight: Weight should be measured within 3 days prior to each dose of avelumab (for determination of the avelumab dose [mg]). |
| 6. | Contraception Check: Female patients who are of childbearing potential will need to affirm that they meet the criteria for correct use of the selected methods of contraception. The investigator or his or her designee will discuss with the patient the need to use the selected contraception methods consistently and correctly and document such conversations in the patient's chart. In addition, the investigator or his or her designee will instruct the patient to call immediately if the selected contraception methods are discontinued, or if pregnancy is known or suspected in the patient or the male patient's partner. See Section 4.3.1 . |
| 7. | Hematology and Blood Chemistry: Required tests are listed in Table 7 . May also be performed when clinically indicated. |
| 8. | Thyroid Function and ACTH Tests: Free T4, TSH, and ACTH tests will be performed on Day 1 of every 2 cycles (8 weeks). Additional tests should be performed when clinically indicated. See Table 7 . |
| 9. | Serum/Urine Pregnancy Test: For female patients of childbearing potential, a serum or urine pregnancy test, with sensitivity of at least 25 mIU/mL, will be routinely repeated prior to each avelumab dose during the active treatment period, at the End of Treatment/Withdrawal visit, and additionally whenever one menstrual cycle is missed or when potential pregnancy is otherwise suspected. Additional pregnancy tests may also be undertaken if requested by Institutional Review Board (IRB)/Ethics Committees (ECs) or if required by local regulations. Results of the pregnancy test should be available prior to each dosing. See Section 7.1.1 . |
| 10. | 12-Lead Electrocardiogram (ECG): To be performed as clinically indicated. Clinically significant new findings seen on follow-up ECGs should be recorded as adverse events. |
| 11. | Tumor Assessments: Tumor assessments will be performed at a frequency as per local standard of care and when progression is suspected. The tumor assessment data will no longer be entered into the CRF and radiologic images will no longer be submitted for central imaging review. |
| 12. | Adverse Events: Adverse events (AE) should be documented and recorded at each visit using National Cancer Institute (NCI) Common Terminology Criteria for Adverse Events (CTCAE) version 4.03. For serious adverse events (SAEs), the active reporting period to Pfizer or its designated representative begins from the time that the patient provides informed consent, which is obtained prior to the patient's participation in the study, ie, prior to undergoing any study-related procedure and/or receiving study treatment, through and including 90 calendar days after the last administration of the study treatment. SAEs occurring to a patient after the active reporting period has ended should be reported to the sponsor if the investigator becomes aware of them; at a minimum, all SAEs that the investigator believes have at least a reasonable possibility of being related to study treatment are to be reported to the sponsor. AEs (serious and non-serious) should continue to be recorded on the Case Report Form (CRF) through and including 90 calendar days after the last administration of avelumab. If a patient begins a new anticancer therapy, the AE reporting period for non-serious AEs ends at the time the new treatment is started. Death must be reported if it occurs during the SAE reporting period after the last dose of study treatment, irrespective of any intervening treatment. |
| 13. | Concomitant Medications/Treatments: Concomitant medications and treatments should only be recorded in the CRF if associated with treatment for an AE. |
| 14. | Avelumab Treatment: Avelumab (10 mg/kg) will be given as a 1 hour intravenous infusion every 2 weeks. Patients should be weighed within 3 days prior to each dose of avelumab (for determination of the avelumab dose [mg]). All safety assessments must be performed and results reviewed by the treating physician prior to avelumab administration. Patients with disease progression who are continuing to derive clinical benefit from study treatment will be eligible to continue with avelumab provided that the treating physician has determined that the benefit/risk for doing so is favorable (See Section 5.4.1). |

TABLE OF CONTENTS

| | |
|---|----|
| PROTOCOL SUMMARY | 19 |
| SCHEDULE OF ACTIVITIES..... | 28 |
| LIST OF TABLES | 46 |
| LIST OF FIGURES | 46 |
| APPENDICES | 47 |
| 1. INTRODUCTION | 48 |
| 1.1. Mechanism of Action/Indication..... | 48 |
| 1.2. Background and Rationale | 48 |
| 1.2.1. Urothelial Cancer..... | 48 |

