| 
If a patient begins a new anticancer therapy, the AE reporting period for non-serious AEs ends at the time the new treatment is started. Death must be reported if it occurs during the SAE reporting period after the last dose of study treatment, irrespective of any intervening treatment.
 |
| 
18. Day 15 Assessments for Arm B: Remote contact (eg, telephone) or in-clinic visit for collection of interim AEs and changes in concomitant medications and treatments, if any. A follow-up in-clinic visit should be scheduled if clinically indicated.
 |
| 
19. Concomitant Medications/Treatments: Concomitant medications and treatments will be recorded for all patients from 28 days prior to the start of study treatment and up to 90 days after the last dose of study treatment (Arm A) or 90 days after the EOT visit (Arm B). If a patient begins a new anti-cancer therapy, reporting of concomitant medications should end at the time the new cancer therapy is started; see Section 5.9 for additional details. All concomitant medications will be recorded in the CRF including supportive care drugs (eg, anti-emetic treatment and prophylaxis), the drugs used to treat adverse events or chronic diseases, and non-drug supportive interventions (eg, transfusions). Concomitant medications should be reviewed at each study visit, and any prohibited treatments (as described in Section 5.9) should be discussed with the patient and appropriately managed.
 |
| 
20. NCCN-FACT FBISI-18, EQ-5D-5L: All patients will complete these self-administered questionnaires on Day 1 of each cycle. Patients must complete each questionnaire at the clinic prior to any study or medical procedure.
 |
| 
21. Randomization: An interactive response technology (IRT) system will be used for randomization to a treatment arm as described in Section 5.1. Patients meeting all entry criteria will be randomized and, if randomized to Arm A, will be administered the first dose of avelumab within 3 days after randomization.
 |

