| Other Samplings | | | | | |
| Banked Blood Biospecimens for Exploratory Assessments ¹⁸ | X | | | | |
| De Novo Tumor Biopsy ¹⁹ | X | | | | |

| Visit Identifiers ¹ | End of Treatment/ Withdrawal (±3 days) ² | Follow-up ³ | | | Long-Term every 3 months ±14 days) |
|---|---|---|---|---|--|
| | | Short-Term | | | |
| | | 30 days (±3 days) After Last Dose (Arm A) or EOT/Withdrawal Visit (Arm B) | 60 days (±3 days) After Last Dose (Arm A) or EOT/Withdrawal Visit (Arm B) | 90 days (±3 days) After Last Dose (Arm A) or EOT/Withdrawal Visit (Arm B) | |
| Pharmacokinetics ²⁰ (Arm A ONLY) | X | X | | | |
| Anti-Avelumab Antibodies and Neutralizing ²¹ (Arm A ONLY) | X | X | | | |

ACTH = adrenocorticotrophic hormone; BSC = best supportive care; ECG = electrocardiogram; ECOG = Eastern Cooperative Oncology Group; FFPE = formalin-fixed and paraffin-embedded; Q12W = every 12 weeks

Footnotes for PRIOR TO PROTOCOL AMENDMENT 6: SCHEDULE OF ACTIVITIES FOR END OF TREATMENT/WITHDRAWAL AND FOLLOW-UP PERIODS

- Visit Identifiers:** Acceptable time windows for performing each assessment are described in the column headers. Per the visit time window, laboratory tests may be performed up to 3 days prior to the scheduled clinic visit so that results will be available for review.
- End of Treatment/Withdrawal:** Obtain these assessments if not completed in the prior week, except for tumor assessments, which need not be repeated if performed within the prior 6 weeks.
- Short- and Long-Term Follow-up:** All patients will be followed for safety every 30 days (±3 days) through 90 days after the last dose of study treatment (Arm A) or 30 through 90 days after the End of Treatment (EOT) visit (Arm B), or until the time of initiation of new anticancer treatment. Beyond the 90 days until the end of the study (long-term follow-up), all patients will be followed every 3 months after the last study clinic visit (±14 days) for survival, tumor assessment, and new systemic anticancer treatment; additional timepoints to collect survival information may be requested by the Sponsor in preparation for interim and final analyses.
- Physical Examination:** Includes an examination of major body systems.
- Vital Signs and Weight:** Vital signs to include blood pressure and pulse rate. Blood pressure and pulse rate should be taken with the patient in the seated position after the patient has been sitting quietly for at least 5 minutes.

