5.9. Concomitant Treatments

Medications or vaccinations specifically prohibited in the [Exclusion Criteria](#) are also not allowed during the active treatment period, except for administration of inactivated vaccines.

If there is a clinical indication for one of these or other medications or vaccinations specifically prohibited during the trial, discontinuation from study therapy or medication/vaccination may be required. The final decision on any supportive therapy or

vaccination rests with the investigator and/or the patient's primary physician. However, the decision to continue the patient on study therapy or medication/vaccination schedule requires the mutual agreement of the investigator, the sponsor, and the patient.

Concomitant treatment considered necessary for the patient's well-being may be given at the discretion of the treating physician.

Concomitant medications, blood products, non-drug interventions, and treatments, including herbal supplements, will be recorded from 28 days prior to the start of study treatment and up to 90 days after the last dose of study treatment (Arm A) or 90 days after the End of Treatment (EOT) visit (Arm B).

All concomitant medications will be recorded in the CRF including supportive care drugs (eg, antiemetic treatment and prophylaxis) and the drugs used to treat adverse events or chronic diseases, and non-drug supportive interventions (eg, transfusions). During study treatment, concomitant medications should be reviewed at each study visit, and any prohibited treatments should be discussed and appropriately managed.

Given that recording of non-serious AEs ends when a patient begins a new anti-cancer therapy ([Section 8.2](#)), recording of concomitant medications associated with these non-serious AEs should also end. However, given that SAEs must continue to be recorded up to 90 days after the last dose of study treatment(s) even if the patient begins a new anti-cancer therapy, concomitant medications associated with these SAEs must also be recorded.

As per Protocol Amendment 6, following the final OS update, concomitant medications/treatments will not be captured in the CRF unless they contribute to or are associated with the treatment for an AE.

Concurrent anticancer therapy with agents is not allowed, other than avelumab in patients randomized to Arm A. Medications intended solely for supportive care (ie, antiemetics, analgesics, megestrol acetate for anorexia) are allowed.

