8.2. Reporting Period

For SAEs, the active reporting period to Pfizer or its designated representative begins from the time that the patient provides informed consent, which is obtained prior to the patient's participation in the study, ie, prior to undergoing any study-related procedure and/or receiving study treatment, through and including 90 calendar days after the last administration of the study treatment (Arm A) or 90 days after the EOT visit (Arm B). SAEs occurring to a patient after the active reporting period has ended should be reported to the sponsor if the investigator becomes aware of them; at a minimum, all SAEs that the investigator believes have at least a reasonable possibility of being related to study treatment are to be reported to the sponsor.

AEs (serious and non-serious) should be recorded on the CRF from the time the patient has taken at least 1 dose of study treatment (Arm A) or from Cycle 1 Day 1 (Arm B) through and including 90 calendar days after the last administration of study treatment (Arm A) or 90 days after the EOT visit (Arm B).

If a patient begins a new anticancer therapy, the AE reporting period for non-serious AEs ends at the time the new treatment is started. Death must be reported if it occurs during the SAE reporting period after the last dose of study treatment, irrespective of any intervening treatment.

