3.5. Safety Endpoints

3.5.1. Adverse events

Treatment-Emergent Adverse Events

Treatment-emergent adverse events (TEAEs) are those events with onset dates occurring during the on-treatment period.

On-treatment period is defined as follows:

- Arm A: time from the first dose of study treatment through minimum (30 days + last dose of study treatment, start day of new anti-cancer drug therapy – 1 day)
- Arm B: time from Cycle 1 Day 1 through minimum (30 days + end date of BSC, start day of new anti-cancer drug therapy – 1 day).

As defined in [Section 3.4.1](#), ‘End date of BSC’ is the date of completion or discontinuation as collected in the ‘Disposition - Treatment Phase’ eCRF page.

The start day of new anti-cancer drug therapy after the first dose of study treatment is derived as outlined in [Section 5.2.5](#).

Adverse Events of Special Interest (AESIs)

AESIs are immune-related adverse events (irAE) and infusion-related reactions (IRRs). The criteria for classification of an AE as an irAE or IRR are described in [Appendix 1](#) and [Appendix 2](#), respectively.

3-Tier Adverse Events

It should be recognized that most studies are not designed to reliably demonstrate a causal relationship between the use of a pharmaceutical product and an adverse event or a group of adverse events. Except for select events in unique situations, studies do not employ formal adjudication procedures for the purpose of event classification. As such, safety analyses are generally considered as an exploratory analysis and its purpose is to generate hypotheses for further investigation. The 3-tier approach facilitates these exploratory analyses.

Adverse events and clusters of adverse events, of any causality and treatment-related, will also be summarized following a 3-tier approach. Under this approach, AEs are classified into 1 of 3 tiers.

Tier-1 events: These are pre-specified events or clusters of events of clinical importance and will be described in the Safety Review Plan.

Tier-2 events: These are events that are not Tier-1 but are “common”. A MedDRA PT is defined as a Tier-2 event if it is reported by

- a) at least 10% of patients with any grade in any treatment arm, or
- b) at least 5% of patients with Grade 3, 4 or 5 in any treatment arm.

Tier-3 events: All other AEs that are classified neither as Tier-1 nor Tier-2.

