6.6.4. Other significant adverse events

The frequency (number and percentage) of patients with each of the following will be presented for irAEs, by treatment arm:

- irAEs leading to death, by Cluster and PT
- irAEs, by Cluster and PT
- irAEs, Grade ≥ 3 , by Cluster and PT
- irAEs leading to discontinuation of avelumab, by Cluster and PT
- irAEs leading to discontinuation of BSC, by Cluster and PT
- Serious irAEs, by Cluster and PT

The listing of all irAEs will also be provided with the relevant information with a flag for irAEs with onset outside of the on-treatment period.

The frequency (number and percentage) of patients with each of the following will be presented for IRRs, by treatment arm:

- IRRs leading to death, by PT
- IRRs, by PT
- IRRs, Grade ≥ 3 , by PT
- IRRs leading to discontinuation of avelumab, by PT
- Serious IRRs, by PT
- Time related to first onset of an IRR (infusion 1, infusion 2, infusion 3, infusion 4 or later).

The listing of all IRRs will also be provided with the relevant information with a flag for IRRs with onset outside of the on-treatment period.

In addition, the following analyses will be presented for irAEs (as defined in [Appendix 1](#)) and Tier-2 events separately. CIs for risk difference will be calculated based on the unconditional exact method by [Santner and Snell \(1980\)](#). No additional analyses will be presented for Tier-3 AEs.

- Frequency (number and percentage) of patients with each of the following by treatment arm and PT or Clustered Term:
 - Tier-2 AEs
 - Tier-2 AEs Grade ≥ 3
- Point estimate for risk difference and 95% CI for risk difference (experimental arm vs comparator arm) for each of the following by PT or Clustered Term:
 - irAEs
 - irAEs Grade ≥ 3
 - Tier-2 AEs
 - Tier-2 AEs Grade ≥ 3
- CIs reported are not adjusted for multiplicity and should be used for screening purposes only. The 95% CIs are provided to help gauge the precision of the estimates for the risk difference and should be used for estimation purposes only.

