9. APPENDICES

Appendix 1. Immune-Related Adverse Events

The MedDRA PTs and clusters for irAEs are defined in the Safety Review Plan (SRP) for avelumab.

Immune-related AEs (irAEs) will be programmatically identified as outlined in Table 16. This case definition is hierarchical, ie, each step is only checked for patients and events that have already met the prior step.

Table 16. Case Definition for irAEs

Step	Selection Criteria	Additional Notes
1	Event selected based on a list of pre-specified MedDRA PTs within clusters. These are included in the SRP as Tier1 events (Immune-mediated xxxx). If AE matches the list, then it is in for the next step	
2	AE onset during 1 st study drug administration or anytime thereafter through 90 days after last dose of study treatment.	This is regardless of start of new anti-cancer drug therapy and regardless of TEAE classifications
3	Answer in the AEECRF page to 'Was another treatment given because of the occurrence of the event' is 'YES'	
4	AE treated with corticosteroids or other immunosuppressant therapy. For endocrinopathies only: AE required hormone replacement	Look in the conmed pages for AE identifiers that match the AEs from Step 3. For each of such AEs if A) OR B) OR C) below are met then the AE is in for the next step A) conmed ATC code is in (H02A, H02B, D07, A01AC, S01BA, S01BB, L04AA, L04AB, L04AC, L04AD, L04AX, A07EA) and AEPT is in any of the irAE clusters. B) conmed ATC code is in (H03A, H03B) and AEPT is in one of the irAE clusters associated with "Immune-mediated endocrinopathies" C) conmed ATC code is A10A and AEPT is in the irAE cluster associated with "Immune-mediated endocrinopathies: Type I Diabetes Mellitus"

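### The irAE count runs to day 90 regardless of new anti-cancer therapy, so serious immune events from a next-line checkpoint inhibitor can be credited to the randomised arm; the SAP should also show the comparison ending at new therapy

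*Protocol*

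**What the plan says.** **Collection (protocol).** Section 8.2 and the adverse-event footnotes of the Schedules of Activities state: "If a patient begins a new anticancer therapy, the AE reporting period for non-serious AEs ends at the time the new treatment is started". SAE reporting continues through "90 calendar days after the last administration of the study treatment (Arm A) or 90 days after the EOT visit (Arm B"), with no cut at new therapy. Section 5.9 adds that "concomitant medications associated with these SAEs must also be recorded". Scheduled safety follow-up visits are a different matter. Footnote 3 of the end-of-treatment and follow-up schedule runs them to day 90 "or until the time of initiation of new anticancer treatment".

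**Counting (SAP).** Appendix 1, Table 16, Step 2 accepts onset during the first administration or "anytime thereafter through 90 days after last dose of study treatment", with the note: "This is regardless of start of new anti-cancer drug therapy and regardless of TEAE classifications". SAP 3.4.1 treats BSC as a study drug and takes its end date as the last dose in Arm B, so the window applies to both arms.

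**Use (SAP 6.6.4).** irAEs are tabulated by arm. For irAEs and Grade ≥3 irAEs the plan adds "Point estimate for risk difference and 95% CI for risk difference (experimental arm vs comparator arm"). Serious irAEs are tabulated by arm without a risk difference.

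**Competing rule (SAP).** In 3.5.1 and 5.2.7 the on-treatment period ends at the earlier of 30 days after last study treatment and "start day of new anti-cancer drug therapy – 1 day". Section 5.2.7 says safety data outside it are listed but not summarised. Section 6.6.1 bases AE analyses on treatment-emergent events unless something else is specified.

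**The concern.** irAEs are named as an important risk of avelumab in protocol section 1.3, so the reader of the safety tables wants the excess that avelumab causes over BSC. BSC should contribute few true irAEs. A patient who leaves BSC and starts a PD-1 or PD-L1 inhibitor can have serious pneumonitis or hepatitis before day 90, and the Appendix 1 rule can count that event under BSC. The same can happen in Arm A, where the event is added to avelumab's count.

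Two features make the late part of the window hard to interpret. It mixes toxicity of the randomised treatment with toxicity of whatever came next. It is also selective by seriousness, because non-serious events are no longer collected. One result is that avelumab's own late non-serious irAEs are missed once an Arm A patient starts new therapy, which lowers Arm A's any-grade count.

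Separately, the SAP does not say clearly whether the on-treatment period or the Appendix 1 window decides which irAEs enter the summaries.

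**Working it through.** **1. Can such an event pass the irAE algorithm?** Take an Arm B patient who starts a checkpoint inhibitor after BSC ends and has serious, steroid-treated pneumonitis before day 90.

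| Appendix 1 step | Result | Reason |
|---|---|---|
| 1. Term on the irAE list | Assumed met | The list is in the Safety Review Plan, not shown here |
| 2. Onset window | Met | Day 90 not passed; new therapy ignored |
| 3. Treatment given for the event | Met | Serious events are still recorded |
| 4. Corticosteroid or other immunosuppressant | Met | Protocol 5.9 keeps medications linked to SAEs |
| 5. Etiology and pathology | Usually met | 5A asks only whether a cause other than immune-mediated is clear; if pathology confirms an immune mechanism, the event stays in whatever 5A says |

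A non-serious event in the same patient would not be collected, so it never reaches Step 1.

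**2. Which window governs?** SAP 6.6.1 gives way where something else is specified. Appendix 1 specifies a different window and says its final data set is the basis of the irAE analyses. On that reading Appendix 1 governs. If the last sentence of 5.2.7 governed instead, the 90-day rule in Step 2 would have no effect on any summary table. Appendix 1 is the more natural reading, but the text leaves a conflict.

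**3. Size.** The documents state no figure on this point, so this is illustration only. Let p be the irAE risk without leakage, c the share starting a checkpoint inhibitor inside the window, and s the serious irAE risk among those patients:

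observed RD = [pA + (1 − pA)·cA·s] − [pB + (1 − pB)·cB·s]

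Inputs:
- pA = 71/717 = 9.9% (treatment-related potential irAEs in the phase 1 expansion cohorts, protocol 1.2.2.1).
- pB = 0, an assumption.
- cA = 0 or 20%, cB = 10–50%, s = 1–5%. All are assumptions; the documents give none of them.
- n = 334 per arm (668 at 1:1).

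| cA | cB | s | Shift in RD (points) |
|---|---|---|---|
| 0 | 10% | 1% | −0.10 × 0.01 = −0.1 |
| 0 | 30% | 3% | −0.30 × 0.03 = −0.9 |
| 0 | 50% | 5% | −0.50 × 0.05 = −2.5 |
| 20% | 10% | 5% | 0.901 × 0.20 × 0.05 − 0.10 × 0.05 = +0.4 |
| 20% | 50% | 5% | 0.901 × 0.20 × 0.05 − 0.50 × 0.05 = −1.6 |

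Approximate 95% CI half-width for the RD: 1.96 × √(0.099 × 0.901 / 334) = 3.2 points.

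**4. A narrower range for s.** Protocol 1.2.2.1 lists treatment-related serious pneumonitis in 6, autoimmune hepatitis in 3 and colitis in 2 of 717 patients. That is 6/717 = 0.8% for pneumonitis alone and at most 11/717 = 1.5% for the three together, since patients may overlap. These rates cover the whole observation period, so they are generous for part of a 90-day window. With cA = 0 and an assumed cB of 20–45%, the leak is 0.20 × 0.008 = 0.16 points to 0.45 × 0.015 = 0.675 points. In 334 patients that is about 0.5 to 2.3 patients.

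**The case against.** A reader might infer that the rule necessarily shrinks avelumab's irAE excess and so biases the comparison in the drug's favour. The documents do not support that as a certainty. Step 2 applies equally to Arm A, and no section gives next-line checkpoint-inhibitor use by arm; with more use in Arm A the sign reverses, as the +0.4 row shows. Shrinkage is plausible. Arm A may stay on avelumab after progression or be re-treated with it (protocol 5.4.1), Arm B has no equivalent before the crossover amendment, and the amendment log mentions a US accelerated approval of a checkpoint inhibitor. None of this says how often, or how soon, such drugs were used in a multinational trial.

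A reader might also set the 0.16–0.675 point leak against a 1.5-point serious-event rate and call it a loss of roughly 10–45%. SAP 6.6.4 plans no risk difference for serious irAEs, so that ratio describes no planned contrast. The documents give no overall Grade ≥3 irAE rate from which to size the nearest planned one.

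There are partial safeguards. In Step 5A an investigator can attribute the event to prior or concomitant medication, and medical review may refine the final data set. Neither sets a rule for events after new therapy, so they reduce the leak without closing it. The SAP also calls its safety analyses exploratory and limits these intervals to screening and estimation.

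The strongest argument is that the 90-day rule looks deliberate, because it keeps late avelumab irAEs in view. That stands, and it is why the rule should be supplemented and not replaced.

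**Conclusion.** The concern holds in a limited form. As written, the irAE frequencies and the any-grade and Grade ≥3 irAE risk differences can include serious immune events caused by a next-line checkpoint inhibitor and credit them to the randomised arm. After new therapy that part of the window collects serious events only. The SAP also needs to resolve which window governs these tables.

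Direction and size are not established. Under the assumed ranges the any-grade risk difference moves by −2.5 to +0.4 points. With serious-event rates near the phase 1 figures and no such use in Arm A, it falls by well under one point, so the effect on the any-grade contrast is probably small. The Grade ≥3 contrast may be more sensitive in relative terms, since its base is smaller and serious events are more likely to be Grade ≥3, but that cannot be sized from the documents. This is a cheap improvement of low priority; the documents do not demonstrate a bias.

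**What to change.** 1. Keep the 90-day irAE analysis, and state in SAP 5.2.7, 6.6.1 and Appendix 1 that Appendix 1 governs it over the on-treatment rule.
2. In SAP 6.6.4, add a second between-arm table of irAEs and Grade ≥3 irAEs with risk differences and 95% CIs. In both arms its window ends at the earlier of 90 days after last study treatment and the day before new anti-cancer drug therapy, using the start date already derived in SAP 5.2.5.
3. Tabulate irAEs with onset after new therapy by arm and next-line drug class, with a footnote that only serious events were collected in that period.

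The cost is one or two extra safety tables and a few lines of text. No new data are needed, because follow-up cancer therapy is already captured on the eCRF. The drawback is that the table ending at new therapy omits late avelumab irAEs with later onset. These remain in the 90-day analysis and in the separate tabulation.
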